**Probable:**

- Reasonable temporal relationship with investigational product use.
- Likely to be known reaction to agent or chemical group, or predicted by known pharmacology.
- Event cannot easily be explained by subject's clinical state or other factors.

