#### 3.1 SAFETY ENDPOINTS

The primary safety parameter in this study is the incidence and severity of treatment-emergent and treatment-related adverse events (AEs), both systemic and ocular adverse events in subjects with inflammation due to active non-infectious anterior uveitis.

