## 7 SAFETY AND EFFICACY VARIABLES

### 7.1 SAFETY VARIABLE

Incidence and severity of treatment-related AEs and SAEs, both systemic and ocular reported adverse events.

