**Suspected Adverse Reaction (SAR):**

Any AE for which there is a reasonable possibility that the drug caused the AE. For the purposes of IND safety reporting, “reasonable possibility” means there is evidence to suggest a causal relationship between the drug and the AE. A SAR implies a lesser degree of certainty about causality than adverse reaction, which means any AE caused by a drug.

**Unexpected:** An AE or SAR is considered “unexpected” if it is not listed in the Investigator’s Brochure or is not listed at the specificity or severity that has been observed; or, if an Investigator’s Brochure is not required or available, is not consistent with the risk information described in the general investigational plan or elsewhere in the current application.

**Life-threatening:** An AE or SAR is considered “life-threatening” if, in the view of either the Investigator or sponsor, its occurrence places the patient or subject at immediate risk of death. It does not include an AE or suspected adverse reaction that, had it occurred in a more severe form, might have caused death.

**A SERIOUS ADVERSE EVENT (SAE)** is any AE or suspected adverse reaction occurring at any dose that:

- Results in death.
- Is life-threatening.

- Results in a persistent or significant incapacity or substantial disruption of the ability to conduct normal life functions.
- Requires inpatient hospitalization.
- Prolongs inpatient hospitalization.
- Is a congenital anomaly/birth defect.
- Is a significant medical event (i.e., one that may jeopardize the subject or may require intervention to prevent one or more of the other outcomes listed above).

**A NON-SERIOUS ADVERSE EVENT** is any AE that does not meet the definitions for SAEs as described above.

Each **AE** will be classified as **SERIOUS or NON-SERIOUS** using the definitions provided above.

The **SEVERITY** of each AE will be classified as **MILD, MODERATE, or SEVERE**. The Investigator will review each event and assess its **RELATIONSHIP** to use of investigational product (unrelated, probably, definitely). The AE will be assessed using the following definitions:

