**Unrelated:**

- Event occurring before dosing.
- Event easily explained by uveitis status.
- Event or intercurrent illness due wholly to factors other than investigational product use.

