**Definite:**

- Distinct temporal relationship with investigational product use.
- Known reaction to agent or chemical group, or predicted by known pharmacology.
- Event cannot be explained by subject's clinical state or other factors.

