## 7.4 PROCEDURES FOR AE REPORTING BY THE INVESTIGATOR

AEs will be monitored throughout the study and will be recorded on the CRF with the date and time of onset, date and time of resolution, severity, seriousness, causality (relationship to use of investigational product), treatment required, and the outcome.

To elicit AEs, simple questions with minimal suggestions or implications should be used as the initial questions at all evaluation points during the trial. For example:

- How have you felt since your last assessment?

- Have you had any health problems since your last assessment?

The severity of each AE should be categorized as mild, moderate, or severe.

The causality of use of investigational product in relation to the AE will be assessed by the Investigator after careful medical consideration and categorized as unrelated, probable, or definite.

If an AE occurs, the Investigator will institute support and/or treat as deemed appropriate. If a non-SAE is unresolved at the time of the last day of the study, an effort will be made to follow up until the AE is resolved or stabilized, the subject is lost to follow-up, or there is some other resolution of the event.

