**NOTE:** If an SAE occurs in any study involving TRS01 that is unexpected and is determined to be related or possibly related to investigational product, all sites will be notified by the sponsor and each site should report it to its IRB.

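### Both 'related' causality levels in section 7.3 list foreknowledge of the reaction as a criterion, so an unforeseen drug-caused event may fit no level and can be left out of the treatment-related AE table

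*Combined protocol and SAP*

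**What the plan says.** Under section 7.4, causality is "categorized as unrelated, probable, or definite". Section 7.3 defines each level by three bullets.

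- **Probable:** plausible timing; "Likely to be known reaction to agent or chemical group, or predicted by known pharmacology"; and no easy explanation from the subject's condition or other factors.
- **Definite:** clear timing; "Known reaction to agent or chemical group, or predicted by known pharmacology"; and no possible explanation from those sources.
- **Unrelated:** onset before dosing; easy explanation by the uveitis; or "Event or intercurrent illness due wholly to factors other than investigational product use".

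Nothing says whether a level's bullets must all be met or whether one is enough.

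Other places use a different standard. Section 7.3 defines a suspected adverse reaction as "Any AE for which there is a reasonable possibility that the drug caused the AE" and defines unexpectedness separately. Section 7.5 provides that for an SAE "that is unexpected and is determined to be related or possibly related to investigational product, all sites will be notified by the sponsor". Section 7.2.1, by contrast, limits suspected adverse reactions to those already in the Investigator's Brochure.

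On endpoints, section 3.1 names both treatment-emergent and treatment-related AEs as the primary safety parameter. Section 7.1 names only the latter: "Incidence and severity of treatment-related AEs and SAEs, both systemic and ocular reported adverse events". Section 9.1.2 lists treatment-emergent AEs by group, but tabulates treatment-related AEs by incidence, intensity and relationship.

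**The concern.** Whether a drug caused an event and whether the event was foreseen are separate questions. Sections 7.3 (in its definitions of suspected and unexpected reactions) and 7.5 keep them apart, but the Probable and Definite criteria merge them. For a product that section 1 presents as a novel approach, an unforeseen reaction is a finding that a Phase I/IIa safety trial should be able to record as related.

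The rating carries more weight here than in a controlled trial. Both groups receive TRS01, at two concentrations, and there is no vehicle group against which an excess of events could show regardless of attribution. If investigators rate such an event differently, or rate it Unrelated for want of a better fit, the tabulated treatment-related incidence is too low and not comparable between sites.

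**Working it through.** The plan gives no figure to reproduce: section 9.2 states that no formal sample size estimation was done. The check is of definitions, followed through to the planned outputs.

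**Step 1. Test event.** Take an AE caused by TRS01 with onset during dosing and clear timing. No other factor explains it. It is not a known reaction to the agent or its chemical group, and known pharmacology does not predict it.

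| Level | Timing | Foreknowledge | No other explanation | Level met if bullets are joint? |
|---|---|---|---|---|
| Probable | met | not met | met | no |
| Definite | met | not met | met | no |

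For Unrelated, onset was not before dosing, uveitis does not easily explain the event, and it is not wholly due to other factors. None of the three bullets is met. On the joint reading of Probable and Definite, the event has no level.

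**Step 2. Which reading is workable?** The Unrelated bullets must be alternatives, since onset before dosing is sufficient by itself. If the Probable and Definite bullets were alternatives too:

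- timing alone would satisfy Probable for an event during four-times-daily dosing, so one easily explained by uveitis would meet both Unrelated and Probable;
- a known reaction would satisfy Definite whatever its timing.

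The levels would overlap. The joint reading avoids this and is the more workable, but the protocol does not state it.

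**Step 3. Follow the event to the outputs.**

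- If rated Probable: it is in the treatment-related table.
- If rated Unrelated or left unrated: it is absent from that table but present in the treatment-emergent listing.
- If serious: section 7.5 requires a report to the sponsor within 24 hours whatever the causality.

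**Step 4. Compare with section 7.5.** The all-sites notice needs an SAE that is both unexpected and related or possibly related. The scale has no possible level. Unexpected means absent from the Investigator's Brochure, or not listed there at the specificity or severity seen. A class reaction missing from the Brochure, or a listed reaction of greater severity, can be unexpected and still meet the foreknowledge criterion. The trigger is therefore narrowed, not closed.

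**Step 5. Scale, on assumed rates only.** Let p be the true rate of such an event. The chance of at least one case among n subjects is 1 − (1 − p)^n, with n = 10 per group (up to 20 subjects, 1:1) or n = 20 overall if both concentrations share the same rate. For p = 10% and n = 20: 1 − 0.9^20 = 0.88.

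| Assumed p | n = 10 | n = 20 | Expected cases in 20 (20p) |
|---|---|---|---|
| 5% | 0.40 | 0.64 | 1 |
| 10% | 0.65 | 0.88 | 2 |
| 20% | 0.89 | 0.99 | 4 |
| 30% | 0.97 | >0.99 | 6 |

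Applied literally and jointly, the scale puts none of these cases in the treatment-related table. For example, 3/10 (30%, exact 95% CI 6.7% to 65.2%) could appear as 0/10.

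**The case against.** The strongest reply is that the bullets are features to be weighed. Section 7.4 leaves the rating to the Investigator's medical judgement, and one of the three levels must be chosen. The test event fails every Unrelated bullet and meets two of three for Probable, so Probable is the closest fit. This stands. A reader might infer that a new toxicity cannot be rated related, but the documents do not support that: the joint rule is not written, and an investigator may still choose Probable. What remains is that nothing directs the investigator to do so, and two sites may differ.

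The criterion is also broader than it may look. It accepts reactions known for the chemical group or predicted by pharmacology, so novelty alone does not fail it. How many events would fall outside cannot be judged, because the relevant pharmacology is redacted and the Investigator's Brochure is not available. This stands too, and limits any claim about size.

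The event does not vanish from the safety results. Treatment-emergent AEs are part of the primary parameter in section 3.1 and are listed by group. Section 7.2.1 says that ocular and non-ocular AEs will be summarized separately. Slit-lamp, IOP, ophthalmoscopy and acuity results are summarized whatever the attribution. With about 10 subjects per group, a cluster could be seen in a listing. All true, but a listing is not an incidence result.

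Finally, one might say that the alternative reading makes every AE in the 28 dosing days Probable on timing alone. That goes too far, since Unrelated still claims events easily explained by uveitis or wholly due to other factors. The reading creates overlap, not a blanket rating.

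**Conclusion.** The point holds as a defect in the causality definitions that should be fixed. Foreknowledge is listed as a criterion for both related levels, the way the criteria combine is not stated, and on the more workable reading an unforeseen drug-caused event has no level. It can then be rated inconsistently and be left out of the treatment-related incidence table. The criterion also conflicts with the reasonable-possibility definition in the same section, and section 7.2.1 adds a similar restriction through the Investigator's Brochure.

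Three stronger inferences are not supported:

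- that treatment-related incidence is the whole primary parameter, since section 3.1 also includes treatment-emergent AEs;
- that the notice for unexpected related SAEs is nearly closed, since it is only narrowed;
- that 0/10 in place of 3/10 is a predicted result, since those counts are assumed for illustration.

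The conclusion rests on the joint reading and on the outputs specified in section 9.1.2. Section 9.1 defers to a Statistical Analysis Plan. If that adds a treatment-emergent incidence table, the effect on the results shrinks, but the gap in the rating scale remains.

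**What to change.** Amend section 7.3 as follows:

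1. Make a known or pharmacologically predicted reaction supporting evidence for Probable and Definite, not a condition.
2. State that plausible timing together with no better alternative explanation is enough for a related rating.
3. State for each level whether its bullets apply jointly or as alternatives.
4. Reconcile the suspected-adverse-reaction wording in sections 7.2.1 and 7.3, the causality levels in section 7.3, and the related or possibly related wording in section 7.5.

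The cost is about one paragraph of amendment plus eCRF completion guidance. It should be in place before events are rated, because later re-rating would be retrospective. The related-AE count may come out slightly higher.

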**Definite:**

- Distinct temporal relationship with investigational product use.
- Known reaction to agent or chemical group, or predicted by known pharmacology.
- Event cannot be explained by subject's clinical state or other factors.

## 7.4 PROCEDURES FOR AE REPORTING BY THE INVESTIGATOR

AEs will be monitored throughout the study and will be recorded on the CRF with the date and time of onset, date and time of resolution, severity, seriousness, causality (relationship to use of investigational product), treatment required, and the outcome.

To elicit AEs, simple questions with minimal suggestions or implications should be used as the initial questions at all evaluation points during the trial. For example:

- How have you felt since your last assessment?

- Have you had any health problems since your last assessment?

The severity of each AE should be categorized as mild, moderate, or severe.

The causality of use of investigational product in relation to the AE will be assessed by the Investigator after careful medical consideration and categorized as unrelated, probable, or definite.

If an AE occurs, the Investigator will institute support and/or treat as deemed appropriate. If a non-SAE is unresolved at the time of the last day of the study, an effort will be made to follow up until the AE is resolved or stabilized, the subject is lost to follow-up, or there is some other resolution of the event.

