Safety and Tolerability Outcomes	
Assessment of both systemic and ocular adverse events. AEs will be captured by verbatim term and coded using MedDRA.
 
Relevant clinical findings will also be recorded in the electronic case report form (eCRF) related to the following:
 
 
1. BCVA using ETDRS
 
2. Slit-lamp biomicroscopy, specifically evaluation of intraocular anterior inflammation
 
3. IOP measurement
 
4. Dilated ophthalmoscopy
 
5. Safety parameters of interest include a change from baseline to each visit in ocular signs such as corneal/conjunctival tolerability and IOP measurements.
 

Exploratory Efficacy Measurements	
 
• Anterior chamber cell count by slit-lamp biomicroscopy and by anterior chamber SD-OCT in selected sites.
 
• Anterior chamber flare assessed on slit-lamp biomicroscopy
 
• Change in macular edema by macular OCT
 
• Subject-rated ocular pain assessment
 

Eligibility Criteria	
Inclusion Criteria
 
Individuals of either gender or any race will be eligible for study participation if they are:
 
 
1) 18 years of age or older
 
2) Able to provide informed consent, follow instructions and complete all required study visits for the duration of the study.
 
3) Diagnosed with active non-infectious anterior uveitis requiring an increase or initiation of topical steroids for management of ocular inflammation.
 
 
An eligible subject must have:
 
[REDACTED]
 
[REDACTED]
 
[REDACTED]
 
[REDACTED]
 
[REDACTED]
 
[REDACTED]
 
[REDACTED]
 
[REDACTED]
 
[REDACTED]

- 5) Use adequate birth control by men and women, if of reproductive potential and sexually active. Adequate birth control is defined as agreement to consistently practice an effective and accepted method of contraception throughout the duration of the study and for 2 weeks after the last study visit.
  - a) For females of childbearing potential, adequate birth control methods will be defined as hormonal contraceptives, intrauterine device or double barrier contraception, i.e., condom + diaphragm, condom or diaphragm + spermicidal gel or foam.
  - b) For males, adequate birth control methods will be defined as double barrier contraception, i.e., condom + diaphragm, condom or diaphragm + spermicidal gel or foam.

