### 7.2 SAFETY VARIABLES

Safety measures include AEs/SAEs and clinical assessments from the slit-lamp biomicroscopy findings, IOP, and dilated ophthalmoscopy findings.

AEs and ocular safety measures to be collected in this study are listed in [Table 3](#).

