### 7.2.1 Adverse Events

Adverse events will be collected for subjects following signing of the ICF through the end of the study. The information will include at least a description of the event, onset date, and resolution date, as well as seriousness, severity and relation to study medication (as determined by the Investigator), location (right eye [OD], left eye [OS], both eyes [OU] or other), action taken, and outcome. All AEs will be coded using the Medical Dictionary for Regulatory Activities (MedDRA) dictionary, current version. Ocular and non-ocular AEs will be summarized separately.

*Suspected adverse reactions* (SARs), also known as adverse drug reactions or suspected adverse drug reactions, are AEs considered by the Investigator to be related to the study medication and included in the Investigator's Brochure.

An AE will be considered as an *ocular AE* if the Investigator selects 'OD', 'OS', or 'OU' for the AE eCRF field "Eye(s) affected".

Any AE that causes loss of vision of 15 or more letters (i.e., 3 lines) should be recorded as a serious adverse event (SAE). Examples include endophthalmitis, retinal vascular occlusion, retinal detachment involving the macula/fovea, etc. AEs that cause loss of 15 or more letters (i.e., 3 lines) that are expected to resolve should not be recorded as an SAE. Examples include corneal edema, corneal abrasion, cystoid macular edema or other conditions that are known to affect vision but expected to resolve and not result in a permanent impact on vision.

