#### 9.1.2 Analysis of Safety

Analysis of safety data will be presented for all subjects. AEs will be coded using Medical Dictionary for Regulatory Activities (MedDRA, most current version add in version once finalized) and categorized by system organ class using preferred terms. Treatment emergent AEs will be listed by study group. Treatment related AEs will be tabulated by study group and will be reported by incidence (both number of events and number of subjects) with respect to their intensity and relationship to the IP. Ophthalmoscopy findings will be summarized descriptively. IOP measurements, VA, and slit-lamp biomicroscopy assessments will be summarized as safety outcomes.

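### Section 9.1.2 specifies incidence by arm only for treatment-related AEs, although 3.1 also names treatment-emergent AEs, and the causality scale behind that incidence has no level for a possible relationship

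*Combined protocol and SAP*

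**What the plan says.** **Primary parameter.** Section 3.1 names the "incidence and severity of treatment-emergent and treatment-related adverse events (AEs), both systemic and ocular adverse events". Section 7.1 puts it differently: "Incidence and severity of treatment-related AEs and SAEs, both systemic and ocular reported adverse events". Emergent AEs are not mentioned there. The Synopsis ("Assessment of both systemic and ocular adverse events") and 7.2 ("Safety measures include AEs/SAEs and clinical assessments from the slit-lamp biomicroscopy findings") set no limit by relatedness.

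**Planned output.** Section 9.1.2 states: "Treatment emergent AEs will be listed by study group. Treatment related AEs will be tabulated by study group and will be reported by incidence", counting both events and subjects, "with respect to their intensity and relationship to the IP". Section 7.2.1 adds: "Ocular and non-ocular AEs will be summarized separately". Section 9.1 gives a general number-and-percent rule for categorical measures, says that all data will be listed, and defers to a separate Statistical Analysis Plan.

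**Causality.** Under 7.4, the relationship of each AE to the product is "assessed by the Investigator after careful medical consideration and categorized as unrelated, probable, or definite". Section 7.3 gives the same three grades, with criteria for each. Section 7.3 also defines a suspected adverse reaction by a *reasonable possibility* of causation. The note at the end of 7.5 has all sites notified of unexpected SAEs judged related or *possibly related*.

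**The concern.** Safety and tolerability are the primary objective, and both arms receive TRS01, so no vehicle arm shows the background rate of AEs. The incidence of all treatment-emergent AEs by arm is the AE summary that does not depend on anyone's opinion of cause. It is also the one that the analysis section does not specify. The incidence that is specified depends on a judgement made with a scale that is coarser than the protocol's own language.

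The gap in the scale falls in an awkward place. *Probable* and *definite* both look to a reaction that is known or predicted. An unforeseen reaction to a new product is the kind of event that an early study should bring out, and it is the kind that fits these criteria least well.

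**Working it through.** The plan has no figure to reproduce, since 9.2 states that no formal sample size estimation was done. The check is mainly a comparison of text.

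**1. Parameter against output**

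| Part of the 3.1 parameter | Named in 7.1 | Output in 9.1.2 |
|---|---|---|
| Treatment-related AEs, incidence and severity | Yes | Tabulated by arm: events, subjects, intensity, relationship |
| Treatment-emergent AEs, incidence and severity | No | Listed by arm |

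Section 9.1.2 uses different verbs for the two categories in consecutive sentences, so listing and tabulating are separate outputs. The same contrast supports reading 3.1 as two categories, not as AEs that are both emergent and related.

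**2. The emergent window.** The term is not defined. Under 7.2.1, AEs are collected from consent to the end of the study. Consent, randomization and first dose all fall on Visit 1/Day 1, so the pre-dose part is short. The end matters more: dosing ends at Day 28 and the last visit is Day 70, which leaves 70 − 28 = 42 days whose status is not stated.

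**3. One event taken through the grades.** Take an event after dosing, with reasonable timing, not easily explained by the subject's condition or other factors, and not a likely known or predicted reaction.

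- *Unrelated* (7.3): it did not occur before dosing, uveitis does not easily explain it, and it cannot be called wholly due to other causes. It does not fit.
- *Probable* (7.3): it meets the timing and explanation criteria but fails the known-or-predicted criterion. If the three are joint conditions, it does not fit.
- *Definite* (7.3): the criteria are stricter still. It does not fit.

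The joint reading is the natural one, because the criteria for *probable* and *definite* run in parallel, item by item. Under it, the event has no grade and must be put into one that does not describe it. An event that uveitis easily explains does have a grade, *unrelated*, so the gap does not extend to ordinary disease symptoms.

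**4. Size**

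- Inputs: up to 20 subjects (9.2), allocated 1:1, so 20 / 2 = 10 per arm.
- If *b* subjects in an arm have a clearly related AE, and one more has only an event of the kind in step 3, related incidence is *b*/10 or (*b* + 1)/10. The difference is 1/10 = 10 points. The difference between arms shifts by the same amount. The emergent incidence does not change.
- For scale, exact (Clopper-Pearson) 95% intervals at n = 10 are: 0/10, 0 to 30.8%; 1/10, 0.3 to 44.5%; 2/10, 2.5 to 55.6%. One reclassification is small against sampling error.
- The documents give no rate for such events. Assuming that a subject has one with chance *p*, the chance of at least one in an arm is 1 − (1 − *p*)^10. This is 40%, 65%, 89% and 97% for *p* = 5%, 10%, 20% and 30%.

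**The case against.** The strongest reply is that little is lost. Section 7.2.1 promises a summary of AEs, 9.1 supplies number and percent, and 9.1.2 organizes AEs by system organ class and preferred term. Because consent and first dose fall on the same day, an all-AE summary would start at almost the same point as an emergent one. With about 10 subjects per arm, anyone can count subjects from a by-arm listing. Table layouts belong in the SAP, and the number of causality levels is largely the sponsor's choice.

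Much of this stands, and it limits the point. It does not remove it. None of these sections specifies emergent incidence or severity by arm, and the end of the window is open. Section 3.1 makes that incidence part of the primary parameter, so the protocol's own analysis section should carry it. A sponsor may choose three levels, but then needs to say where a reasonable possibility or a possible relationship falls. No section does so, or says which grades count as treatment-related.

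A reader might also infer that the missing level could hold back SAE reports. The documents do not support that. Investigators report every SAE to the sponsor within 24 hours under 7.5, with no causality filter, and the note on notification does not say who judges relatedness.

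**Conclusion.** The point holds as a mismatch within the protocol text and should be fixed. Section 9.1.2 specifies the incidence of one of the two AE categories in the 3.1 parameter, and that incidence rests on a scale with no place for some post-dose events. The practical effect is limited. One reclassified subject is worth 10 points in an arm of 10, but individual events stay readable in the listings, and graded ocular signs, IOP, BCVA and pain scores do not depend on the scale.

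The conclusion rests on three things: 3.1 names two categories, the criteria for *probable* are joint, and full enrollment is split evenly. The supplied document does not contain the separate SAP, which may already add the table.

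Three stronger readings are not supported:

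- That emergent AEs will go unsummarized. The text shows only that the protocol does not specify their incidence by arm.
- That the wording in 4.2.1 and 5.1.1 on attributing AEs after the first dose is another causality threshold. In 4.2.1 it describes the subject's perception, and in 5.1.1 it decides which staff handle the report. Neither is an investigator rating.
- That coding alone is likely to make the arms look different. This needs assumed event counts and independent coding decisions. Masked investigators at about two sites may well apply one rule to both arms, and 9.1.2 plans no between-arm test of AEs.

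**What to change.** 1. In 9.1.2, tabulate all treatment-emergent AEs by arm, by subjects and events and by severity, regardless of causality. Define emergent as from first dose to a stated end. Align 7.1 with 3.1.
2. In 7.3 and 7.4, add a *possible* level, or a yes/no item for reasonable possibility. Define treatment-related as possible, probable or definite. Keep the reporting by level that 9.1.2 already plans, and state how the criteria within each grade combine.
3. As a wording point only, reconcile the two definitions of a suspected adverse reaction. Section 7.2.1 limits it to related events in the Investigator's Brochure, and 7.3 does not. This does not affect the analysis.

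The cost is one table, one eCRF option and a few sentences. The downside is a somewhat higher related-AE rate that may include some disease symptoms. Reporting by level keeps that visible.
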